#### 3.6.1. Interventions, Observations, or Data Sought:

**Procedure:** Interested individuals will be directed from our recruitment materials (e.g., posters, flyers, business cards, listservs, and electronic media) to visit the study recruitment office (located in the obstetric clinics) to learn more and determine whether they meet the eligibility criteria. If, after learning more about the study, individuals continue to be interested, written informed consent will be obtained and measures will be administered. The potential participant will also be asked to complete a one-week dietary and exercise self-monitoring run-in, turn in a copy of their fitness scores to study staff (if active duty), and receive medical clearance from their obstetrician to participate. (Note: In the unfortunate event that a potential participant miscarries before being randomized, she will have the opportunity to re-screen if she chooses.) Should she continue to be interested, she will return for a Baseline Visit and will be randomized to 1 of 3 conditions: a) GWG-only; b) PPWL-only; or c) GWG+PPWL and oriented to the assigned treatment condition.

**Randomization:** Participants (n=450) will be randomly allocated to 1 of the 3 conditions, using a computer algorithm under the direction of the study biostatistician, [name], with a sequence blocked by screening BMI category (i.e., normal weight, overweight, obese) in order to ensure equal distribution by condition with respect to BMI category. Each condition will have the same number of subjects.

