Being above the GWG recommendations will trigger an increase in the intervention intensity (i.e., moving to the next step—so gaining more weight at any monthly telephone session for those in Step 1 will trigger an increase in the intervention intensity (i.e., moving to Step 2), and any participant in Step 2 who is above the line for 2 consecutive biweekly sessions will trigger an increase in the intervention intensity (i.e., moving to Step 3). This stepped-care approach will have optimal translation to the practice setting, because it allows targeted allocation of resources. Further, this approach allows greatest tailoring of the intervention intensity to the individual (those who have trouble staying within the guidelines early in pregnancy will get more assistance at that time, with a decrease in intervention intensity when their GWG is within the recommended range; those who stay within guidelines early on but require assistance maintaining adherence with guidelines later in their pregnancy receive assistance when they start to experience challenges). A similar stepped-care approach, designed by [name], has been well received by pregnant women in the “Glowing” study.

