**Weight goals:** The GWG goals for each participant will reflect the 2009 IOM guidelines[30]: a) for normal weight women (BMI 18.5-24.9 kg/m^2): 11-16 kgs (25-35 lbs); b) for overweight women (BMI 25.0-29.9 kg/m^2): 7-11.5 kgs (15-25 lbs); and c) for obese women (BMI 30-39.9 kg/m^2): 5-9 kgs (11-20 lbs) based on their weight collected at their screening appointments. Ongoing weight self-monitoring will be a central feature of the intervention at all steps. Most experts considered frequent weighing a key component to any weight management program (83-86) and it appears to be important in pregnancy-related weight interventions as well. For this reason, participants will be prompted to weigh themselves at least weekly on an electronic scale, which they will be given at baseline. The electronic scale will be issued to the subject as part of treatment on a hand receipt. Due to depreciation of the scale over 21 months of use during the study, the scales would be valued at near zero, and therefore subjects will not be required to return them. The electronic scales are part of the treatment and not considered a form of compensation for participating in the study. Each time a participant weighs, the electronic scale will upload the weight automatically to a secure website. Each week, participants will receive an email from their interventionist with a weight graph tailored to their screening weight BMI and their current weight trajectory as well as personalized feedback from their interventionist about their trajectory. Participants who gain less weight than the guidelines will be instructed to increase their caloric intake and to monitor their weight daily. Study staff will notify Obstetrics staff about participants who gain less weight than the guidelines at two consecutive intervention sessions, but will be retained in the study.

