**Weight goals:** Weight loss from birth to 6-weeks postpartum is fairly standard—approximately 6 kilograms (or 13 pounds)—regardless of pregravid weight category and GWG [29]. For women with a normal pregravid BMI, the PPWL goal (initiated at 6-weeks postpartum) will be to return to the pregravid weight. For women who were overweight or obese pre-pregnancy, the PPWL goal (initiated at 6-weeks postpartum) will be to at least return to their pregravid weight and, if desired, lose up to an additional 5% of their pregravid weight. All participants will be advised to lose weight at a rate of approximately 1 pound per week, which has been shown to not have adverse effects on infant growth or breast milk production. All women will be given a tailored graph indicating the recommended PPWL trajectory. They will be prompted to weigh themselves at least weekly on the electronic scale provided at baseline (which will upload the weight automatically to a secure website). The electronic scale will be issued to the subject as part of treatment on a hand receipt. Due to depreciation of the scale over 21 months of use during the study, the scales would be valued at near zero, and therefore subjects will not be required to return them. The electronic scales are part of the treatment and not considered a form of compensation for participating in the study. These weights will be plotted on a graph and emailed to them weekly along

with personalized feedback from their interventionist about their weight trajectory. The graph will clearly identify weight losses that are both greater than recommended and below recommendations. Participants who are losing weight faster than expected will be instructed to increase their caloric intake and to monitor their weight daily. Participants who lose more weight than expected at 2 consecutive monthly intervention sessions will be referred to their obstetrician for guidance, but will be retained in the study.

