#### **6.2. Sample size estimation/power analysis:**

The study aims to enroll 755 (with the intent for 450 subjects completing the study) participants, 150 participants in each group. This distribution will provide a diverse representation within each intervention group and will provide the necessary information for data and power analysis.

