#### **6.3. Statistical Analysis:**

All of the analyses will be performed with SASv9.4. Data will be examined for distributional normality and outliers prior to any analyses. Descriptive statistics will be generated for all variables of interest included in the analysis, overall and by treatment arm. Univariate comparisons will consist of t-test, chi-square test, ANOVA, and their respective non-parametric counterparts if needed, for continuous/categorical variables respectively. Primary analyses will be intention-to-treat, without regard to intervention adherence. We will use multivariable linear ANCOVA-like regression models for continuous outcomes, to model and compare

the GWG (Hypothesis 1) and PPWL (Hypothesis 2), in the 3 arms. Using these models, treatment effects will be estimated and tested by comparing change in group-specific means at the final prenatal visit and 12-months postpartum conservatively adjusting for baseline differences (which will be minimal by virtue of randomization) and in the case of hypothesis 2 for 6-weeks postpartum weight differences. Randomization validity will be assessed by comparing arms on baseline measures using chi-square tests, ANOVAs and other appropriate tests. If imbalances are found, we will consider adjusting the between-group analyses for potential confounders.

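### Stepped care may make the residual variance differ by arm; section 6.3 names no variance structure, so the default single variance could give wrong standard errors for both primary contrasts

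*Combined protocol and SAP*

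**What the plan says.** Section 6.3 (Statistical Analysis) plans intention-to-treat linear models of the ANCOVA type for gestational weight gain (Hypothesis 1) and postpartum weight loss (Hypothesis 2) in all three arms. In these models "treatment effects will be estimated and tested by comparing change in group-specific means at the final prenatal visit and 12-months postpartum", with adjustment for baseline and, for Hypothesis 2, for weight at 6 weeks postpartum. The distributional checks named are normality and outliers. Equal variance, robust standard errors and Welch-type tests are not mentioned.

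Section 3.6 gives each hypothesis a single comparator arm: PPWL-only for gestational gain and GWG-only for postpartum loss. Neither section 3.2 nor section 6.3 says whether the two treated arms are each compared with it or are combined.

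Section 3.6.1 describes an intervention that responds to the outcome itself. Women above the gain guideline are moved up a step (Table 1 and the text below it), and the plan says that "this approach allows greatest tailoring of the intervention intensity to the individual". At the other end, "Participants who gain less weight than the guidelines will be instructed to increase their caloric intake". Postpartum, women losing too slowly are moved up a step (Table 2), and "Participants who are losing weight faster than expected will be instructed to increase their caloric intake".

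On numbers, section 3.6.1 states that "Each condition will have the same number of subjects". Section 6.2 gives "150 participants in each group" and says that "The study aims to enroll 755 (with the intent for 450 subjects completing the study) participants". It asserts that this distribution "will provide the necessary information for data and power analysis", but gives no alpha, power, effect size or SD.

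**The concern.** An intervention that restrains high gainers and encourages low gainers is built to narrow the distribution of weight change as well as to shift its mean. Randomization does not protect against the resulting difference in variance, because treatment produces it.

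An ordinary three-arm linear model has one residual variance, estimated from all arms together. For Hypothesis 1, two arms get the gestational intervention and one does not. If the two treated arms are less variable, they pull the pooled variance down. The contrast, however, takes at least half of its error from the comparator. The standard error would then be too small, the 95% interval too narrow and the test too liberal. Both primary analyses use the same kind of model, and nothing in 6.3 guards against unequal variances in either direction.

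**Working it through.** **Plan's own figure.** 3 × 150 = 450. Going from 755 enrolled to 450 completing is a loss of 1 − 450/755 = 40.4%. Without an alpha, power, effect size or SD, no power calculation can be reproduced.

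**Inputs.** n = 150 per arm (6.2) and equal allocation (3.6.1). Assumed: a two-sided 5% test, and q = comparator residual SD divided by treated residual SD, with both treated arms alike and their variance set to 1. The range for q is 1.1 to 1.5, with 1.0 and a value below 1 for reference.

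**Pooled variance from three equal arms:** (2 + q²)/3.

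**Pairwise contrast (one treated arm v comparator).**
- Model variance: [(2 + q²)/3] × 2/150
- True variance: (1 + q²)/150
- Model/true: 2(2 + q²) / [3(1 + q²)]

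**Combined contrast (mean of the two treated arms v comparator).**
- Model variance: [(2 + q²)/3] × (1/300 + 1/150) = (2 + q²)/300
- True variance: 1/300 + q²/150 = (1 + 2q²)/300
- Model/true: (2 + q²)/(1 + 2q²)

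**Real error** = 2[1 − Φ(1.96 × √(model/true))]. For q = 1.25, q² = 1.5625. Pairwise, 7.125/7.6875 = 0.927, with square root 0.963, giving 5.9%. Combined, 3.5625/4.125 = 0.864, with square root 0.929, giving 6.9%.

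| q (comparator/treated SD) | Pairwise: model SE/true SE | Pairwise: real error | Combined: model SE/true SE | Combined: real error |
|---|---|---|---|---|
| 1.0 | 1.000 | 5.0% | 1.000 | 5.0% |
| 1.1 | 0.984 | 5.4% | 0.969 | 5.8% |
| 1.25 | 0.963 | 5.9% | 0.929 | 6.9% |
| 1.5 | 0.934 | 6.7% | 0.879 | 8.5% |
| 1/1.2 (treated more variable) | 1.030 | 4.4% | 1.062 | 3.7% |

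Coverage of the 95% interval is 100% minus the real error, so 93.3% pairwise and 91.5% combined at q = 1.5.

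**Each pair fitted alone, equal numbers.** The two-arm pooled variance is (1 + q²)/2. Times 2/150 it gives (1 + q²)/150, which is the true variance. The standard error is right at any q.

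**Unequal numbers, same total of 450, q = 1.25.** With 130 in the comparator and 160 in each treated arm, the real error is 6.5% pairwise and 7.4% combined, and 5.5% even in a two-arm fit. With 170 and 140, the figures are 5.4%, 6.3% and 4.5%.

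**Simulation check** (three-arm ANCOVA with one covariate, 20,000 runs, 150 per arm). At treated/comparator SD ratios of 0.9, 0.8 and 0.7 (q = 1.11, 1.25, 1.43), ordinary standard errors gave 5.4%, 6.1% and 6.5% pairwise and 5.8%, 7.0% and 7.7% combined. HC3 gave 4.7% to 5.2% throughout.

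**Is the range of q reasonable for Hypothesis 1?** As an illustration with assumed inputs, take gains with mean 14 kg and SD 4 to 6 kg. Remove 25% to 50% of any gain above 16 kg and 0% to 25% of any shortfall below 11 kg (the normal-weight limits in 3.6.1). The resulting q is 1.08 to 1.34. This does not reach 1.5, so the top of the range is a bound and not an expectation.

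**The case against.** A reader might infer that the standard errors are understated for both primary contrasts. The documents do not support that, for four reasons.

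- **No SD is given.** A smaller variance in the treated arms is inferred from how the intervention works. Uneven response to telephone sessions could widen the spread instead, and a pooled standard error would then be too large. This stands, so the finding is conditional.
- **Hypothesis 2 is not the mirror image of Hypothesis 1.** Its comparator, GWG-only, has itself had stepped care through pregnancy, while one of its treated arms, PPWL-only, has not. Postpartum targets also differ by woman: return to her own pregravid weight, with an optional further 5% if she was overweight or obese. The direction is therefore uncertain. A rough model with assumed inputs (retention of mean 5 kg and SD 4 to 6 kg, 25% to 50% of it removed) gave q from 0.89 to 1.43 before covariate adjustment. This also stands.
- **The larger error rates need a 300 v 150 contrast.** The plan never names one. Section 3.6 gives the combined-intervention arm its own role in judging additive or synergistic effects, which argues against merging. The pairwise figures are the safer reading, and a pair fitted alone with equal numbers has no problem. Against this, 6.3 describes models of all three arms, and equal numbers at analysis are not assured: 755 are to be enrolled for 450 completing, and how much of that loss follows randomization is not stated.
- **A common variance is not written in the plan.** It is only the default for such a model. Descriptive statistics by arm are already promised, which would ordinarily show SDs. But describing the SDs does not change the standard error used in the primary test.

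The Hypothesis 1 illustration is also approximate: it uses one BMI group's whole-pregnancy range, while the outcome stops at week 36 or 32. It shows plausibility only.

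**Conclusion.** The point holds as a conditional one. Two-sided feedback on the outcome is documented and acts only in the arms receiving that phase's intervention. Section 6.3, read with its default single variance, has no protection if the spreads differ. A more variable comparator is the likelier case for Hypothesis 1; for Hypothesis 2 the sign is open.

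The effect is modest. It concerns intervals and p-values and leaves the estimated differences alone. The tabulated sizes rest on the assumed SD ratio, equal arms of 150, a two-sided 5% test and a three-arm pooled variance. The change is worth making because one specification covers either direction of unequal variance, and unequal completer numbers as well.

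**What to change.** State in 6.3 that both primary models use one of the following, chosen now and applied whatever the diagnostics show:

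- arm-specific residual variances (SAS PROC MIXED, REPEATED / GROUP=arm, with Satterthwaite degrees of freedom); or
- HC3 standard errors.

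State also whether each hypothesis is tested by pairwise contrasts or by a combined one, and report the SD of weight change by arm beside each mean difference.

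The cost is a line or two of SAP text and one option in SAS. If the variances are in fact equal, the loss of power is negligible: a comparison resting on two arms has about 298 degrees of freedom (2 × 150 − 2) instead of about 447 (450 − 3), and the critical value moves from 1.965 to 1.968. Fixing the method in advance also avoids choosing the standard error after seeing the data.

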### 3.6.8. Instrumentation:

- Contact information
- Demographics: Participants will complete a questionnaire regarding their age, parity, race, and ethnicity.
- Physical Assessment:
  - Weight: At all measurement visits, weight will be recorded in kilograms. Weight will be measured on a calibrated digital scale in duplicate, with the participant wearing light clothing and no shoes. While we will obtain the mother's weight at baseline, we will also obtain self-reported pregravid weight (before the last menstrual period). The difficulty of anticipating when a final weight should be obtained to capture the fullest extent of GWG was considered, and we elected to use an approach that afforded two possible weights that would be available for analytic purposes. The Week 36 weight will be the primary outcome except for mothers who deliver prior to 36 weeks, in which case we will use the Week 32 weight. Thus, we will have a final observation of GWG for all participants, regardless of whether they deliver earlier than 36 weeks.
  - Waist Circumference: As an indicator of subcutaneous and visceral abdominal fat, waist circumference will be measured (recorded in centimeters) using a non-distensible measuring tape and standard protocols for positioning.
  - Height: Height, using a wall-mounted stadiometer, will be recorded in centimeters. BMI will be calculated from measured weight and height.
- Physical Activity: We will assess physical activity, subjectively, using the International Physical Activity Questionnaire, as it has been used in other studies of gestational/postpartum weight management, has been validated against accelerometry, and has good test-retest reliability. We will also assess physical

activity objectively using the Actical accelerometer. Participants will be asked to wear the accelerometer for 7 days, including 2 weekend days and 3 weekdays.

- Weight Gain Recommendations: We will assess knowledge of weight gain recommendations at the Baseline visit, before randomization. One previous study has shown the gestational weight gain expectations, in a civilian population, predicted actual pregnancy weight gain; however, it is not certain whether this finding will replicate in a military population.

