#### **6.1. Outcome Measures:**

The primary study outcomes will be a comparison of GWG from baseline to the final gestational weight (either week 32 or week 36, depending on the delivery date) as well as a comparison of weight loss from 6-week postpartum to 12-months postpartum for the 3 intervention arms.

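### Screening BMI category blocks the randomization, but section 6.3 does not name it in the primary models; the cost is some GWG precision

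*Combined protocol and SAP*

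**What the plan says.** - **Allocation (3.6.1, Randomization).** Participants go to three arms of equal size, "with a sequence blocked by screening BMI category" (normal weight, overweight, obese), "in order to ensure equal distribution by condition with respect to BMI category".
- **Goals (3.6.1, GWG weight goals).** "The GWG goals for each participant will reflect the 2009 IOM guidelines": 11-16 kg, 7-11.5 kg and 5-9 kg for the three categories, set from the screening weight.
- **Outcomes (6.1 and 3.6.8).** The GWG outcome is a "comparison of GWG from baseline to the final gestational weight (either week 32 or week 36, depending on the delivery date". Section 3.6.8 adds: "The Week 36 weight will be the primary outcome except for mothers who deliver prior to 36 weeks". The postpartum outcome (PPWL) is weight loss from 6 weeks to 12 months.
- **Models (6.3).** Both hypotheses use ANCOVA-like linear regression, "conservatively adjusting for baseline differences (which will be minimal by virtue of randomization"; Hypothesis 2 also adjusts for 6-weeks postpartum weight. No other covariate is named here or in 6.0 to 6.2.
- **Further covariates (6.3).** "Randomization validity will be assessed by comparing arms on baseline measures using chi-square tests, ANOVAs and other appropriate tests". Then: "If imbalances are found, we will consider adjusting the between-group analyses for potential confounders". There is no variable list, threshold or timing.

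**The concern.** The plan treats BMI category as important enough to block on and to set weight goals by, but the analysis section does not carry it into the models. The stated way to add covariates is to look for imbalance, and blocking removes imbalance in this factor. An analyst who follows 6.3 literally could therefore fit both primary models without the randomization stratum, and two analysts could fit different models. What is at stake is precision: variation in GWG between BMI categories that the model could explain would stay in the error term.

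**Working it through.** **1. The plan's own figures.** Section 6.2 gives 3 × 150 = 450 completing out of 755 enrolled, so 1 − 450/755 = 40.4% are expected not to complete. It states no alpha, power, SD or effect size, so there is no power figure to reproduce. Below, 80% power at a two-sided 5% level is an assumed starting point.

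**2. Would the baseline test pick up the category?** Simulated 1:1:1 permuted blocks within category (60/34/6% mix, see step 3), followed by a chi-square test of arm by category, 4,000 runs per setting. The plan gives no block size, so 3, 6 and 12 were tried. The test reached p<0.05 in 0 of 4,000 runs in every blocked setting; the smallest p-values were 0.995, 0.95 and 0.83. Simple randomization gave 5.4%. With 755 randomized and 40.4% random dropout, the test among completers fired in at most 0.05% of runs.

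**3. How far apart might the categories be?** Goal midpoints are (11+16)/2 = 13.5, (7+11.5)/2 = 9.25 and (5+9)/2 = 7 kg. The trial's BMI mix is not stated. The background section gives 34% overweight and 6% obese for active duty women; taking the remaining 60% as normal weight:

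- mean = 0.60×13.5 + 0.34×9.25 + 0.06×7 = 11.665 kg
- between-category variance = 0.60×1.835² + 0.34×2.415² + 0.06×4.665² = 5.31 kg²

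**4. Residual-variance cut from adding the category to a model that already has baseline weight.** Baseline weight was built as BMI × height² (assumed height 1.64 m, SD 0.065; BMI uniform within the normal and overweight bands, right-skewed from 30 to 40 in the obese band; 1,000,000 draws). The within-category SD of GWG is assumed to be 4, 5 or 6 kg.

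| Spread of category means relative to goal midpoints | SD 4 | SD 5 | SD 6 |
|---|---|---|---|
| None | 0% | 0% | 0% |
| Half, mix 60/34/6 | 3.0% | 2.0% | 1.4% |
| Half, mix 40/35/25 | 3.2% | 2.1% | 1.5% |
| 80%, mix 60/34/6 | 7.4% | 4.9% | 3.5% |
| Full, mix 60/34/6 | 11.2% | 7.4% | 5.3% |
| Full, mix 40/35/25 | 11.8% | 7.9% | 5.6% |

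A separate trial-level simulation (n = 450, full spread, 60/34/6) agrees. The mean standard error of the two GWG arms against PPWL-only fell from 0.4250 to 0.4007, from 0.5197 to 0.5003 and from 0.6169 to 0.6005 kg. As variance cuts these are 1 − (0.4007/0.4250)² = 11.1%, and likewise 7.3% and 5.2%.

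**5. What a cut c is worth.** Intervals narrow by 1 − √(1−c). The equivalent extra sample is 450/(1−c) − 450. Power is Φ((1.960+0.842)/√(1−c) − 1.960).

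- c = 3%: intervals 1.5% narrower, about 14 participants, power 81.2%
- c = 12%: intervals 6.2% narrower, about 61 participants, power 84.8%

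**6. Type I error.** With no covariate at all, R² = 5.31/(5.31+SD²) = 0.249, 0.175 and 0.129 for SD 4, 5 and 6. The actual level of a nominal 5% test is 2[1 − Φ(1.96/√(1−R²))] = 0.024, 0.031 and 0.036. The reported standard error is too large because it ignores the balance that blocking created. At SD 5 it is 0.5500 against 0.5003, a variance gap of 1 − (0.5003/0.5500)² = 17.3%.

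With baseline weight only, the simulated level was 0.045-0.051 (5,000 runs per setting, block size 6, half and full spread) and 0.042-0.056 over the wider settings of the 4,000-run simulation. The 0.056 came at block size 3. In those same runs the model with the category added, whose t-test is exact in this simulation, gave 0.060, so the excess is simulation noise.

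**The case against.** Section 6.3 commits without condition to adjusting for baseline differences and names no variable, so none is excluded; BMI could be among them. This stands in part. A reader might infer that the plan rules BMI category out, and the text does not say so. It does not name it either, and that is the point made here.

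The baseline tests look for confounders, and a factor balanced by design is not one. It is fair not to fault a confounder check for passing over a precision covariate. Nor is it strictly true that the test can never select the category: step 2 concerns allocation and random dropout, and differential dropout could still produce a difference.

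The gain may be near zero, and most inputs are assumed. That also stands. Full spread is probably too generous. The midpoints are intervention goals, the outcome runs only from baseline to week 36 or 32, and the background section reports overweight and obese women exceeding the guidelines more often (77-84% and 74-83%) than normal weight women (53-71%), which would pull achieved means closer together. The mix is also uncertain, because 3.6.7 admits retirees and dependents as well as active duty women.

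**Conclusion.** The point holds as a minor one. The randomization stratum is not named in either primary model, and the stated route to extra covariates will almost never add it. If baseline weight is in the GWG model, the residual variance given up is 0% to about 3% at up to half the goal-midpoint spread and about 5-12% at full spread, depending on the assumed SD and BMI mix. If no baseline covariate is used, the loss is larger and the test is conservative.

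Three stronger conclusions are tempting and unsupported:

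- **Bias or inflated type I error.** Omitting the stratum causes neither. Inflation would need the model to be chosen after outcomes are seen, and the plan does not say that will happen.
- **A figure for chance flags on other baseline variables.** This would depend on how many variables are tested and at what level. The plan states neither.
- **A loss for Hypothesis 2.** That model already includes 6-weeks postpartum weight, and the postpartum goals in 3.6.1 follow pregravid rather than screening BMI. No precision gain can be derived from the documents; naming the stratum there simply aligns the analysis with the design.

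**What to change.** In 6.3, state that both primary models include screening BMI category (three levels, as randomized) and baseline weight as fixed covariates, whatever the baseline comparisons show. Treat any imbalance-triggered adjustment as a labelled sensitivity analysis. This takes no position on 6-weeks postpartum weight as a Hypothesis 2 covariate; it is measured after randomization and is a separate question.

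The cost is one or two sentences. Both variables are already collected. The category uses 2 degrees of freedom, and baseline weight 1 more if it is not already in the model, out of 450 participants.
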